6.1.1 General definitions

Day 7 assessment

Day 7 assessment refers to information reported by the caregiver after Day 0 and recorded in Day 7 form. Data collected as part of unscheduled visits are also integrated in these forms. If multiple successful follow-up assessments for the same child are recorded within the Day7 database, the most recent follow-up assessment will be used. To limit potential recall bias, assessments conducted far beyond the expected follow-up time will be dropped, i.e. 30 days from Day 0.

Death

A child will be considered deceased if, from Day 7 assessment, his/her status at the time of follow-up is “deceased”. In case of implausible death date (i.e. prior to enrolment date), death will be assumed to be within 7 days of Day0.

Hospitalisation

A child will be considered hospitalised if, from Day 7 assessment, he/she went to a hospital, was admitted overnight or if his/her status at the time of follow-up is “hospitalised”. In case of implausible hospitalisation date (i.e. prior to enrolment date), hospitalisation will be assumed to be within 7 days but after 24hrs of Day0.

Hospitalisation within 24hrs of Day0

For the purpose of primary analysis, a child will be considered admitted to hospital within 24hrs of Day0 consultation if the date of hospitalisation is the same as Day0 date or is one day after Day0 date.

Referral

A child will be considered to be referred (either to a hospital or to an inpatient part of a larger primary healthcare facility) if, at Day0, the research assistant confirms that an urgent referral advice was recorded for the child. If urgency is unknown, referral will be assumed to be urgent.

Antibiotics

Antibiotics will be defined in accordance with the WHO antibiotic point prevalence survey (PPS) methodology [4, 5, 6] and therefore only antibacterials for systemic use will be taken into account.

SpO2 values

SpO₂ should be recorded during the Day0. For the outcomes, the following measures will be taken for spurious and missing SpO₂ values:

- If SpO₂ value is not available, the child will be assumed normoxaemic
- If $70 \leq \text{SpO}_2 < 90\%$, the child will be assumed (with accuracy) to have severe hypoxaemia
- If $40 \leq \text{SpO}_2 < 70\%$, the child will be assumed (with low accuracy) to have severe hypoxaemia
- If $\text{SpO}_2 < 40\%$, the value will be considered spurious (e.g. due to incorrect dataentry) and treated as not available, i.e. the child will be assumed normoxaemic.

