6.1.2 Health, hospitalisation and referral outcomes

6.1.2.1 Proportion of children with a severe complication by Day 7

Severe complication is defined as death or secondary hospitalisation. Secondary hospitalisation refers to any delayed hospitalisation (occurring at any point greater than 24hrs after the Day 0 consultation) and any hospitalisation occurring without a referral. Information on death and hospitalisation will be taken from Day7 follow-up assessment.

Death will be counted in the numerator if death date is within 7 days of Day0 (7th day included). Hospitalisation will be counted in the numerator if the child was not referred at Day0 or hospital admission date is within 7 days of Day0 (7th day included) but after 24hrs of Day0.

The denominator will be all children recruited. Children for whom no death and hospitalisation data are available or withdrew prematurely from the study will be assumed to be alive and not hospitalised by Day7.

6.1.2.2 Proportion of children admitted to hospital within 24 hours of Day 0 consultation and as a result of a referral

Information on hospitalisation will be taken from Day7 follow-up assessment.

Hospitalisation will be counted in the numerator only if the child received a referral advice (as per definition above) at Day0 and hospital admission date is within the end of the following day. The denominator will be all children recruited.

Additionally, the proportion will be calculated and reported using only children who were referred as denominator.

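### The hospitalisation rule for severe complication by Day 7 has no Day 7 limit for children who were not referred

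*SAP*

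**What the plan says.** SAP 6.1.2.1 defines the outcome as "Proportion of children with a severe complication by Day 7". A severe complication is death or secondary hospitalisation. The latter covers admissions more than 24 hours after the Day 0 consultation and "any hospitalisation occurring without a referral".

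The counting rule for admissions is "Hospitalisation will be counted in the numerator if the child was not referred at Day0 or hospital admission date is within 7 days of Day0"; the sentence then adds that the seventh day is included and that the admission must fall after 24 hours. The sentence before it limits deaths to Day 7 for every child. "Information on death and hospitalisation will be taken from Day7 follow-up assessment".

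SAP 6.1.1 governs which assessments supply the data. Where there are several, "the most recent follow-up assessment will be used". The only cut on timing is that "assessments conducted far beyond the expected follow-up time will be dropped, i.e. 30 days from Day 0". A child also counts as hospitalised if that is the status when the call is made.

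The planned call window is Day 7 to Day 10 (Protocol 7.1.1; SAP 3.8). Protocol 7.1.1 describes the follow-up data as covering hospitalisation and death from Day 0 to Day 7.

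**The concern.** The rule has two branches joined by 'or'. The first, not referred at Day 0, carries no date condition. The second carries both the 7-day limit and the 24-hour condition. Nothing else in the SAP limits the admission date for the first branch. Section 6.1.2.1 does not limit the follow-up date either, whereas referral completion (6.1.2.5) and cure (6.1.2.7) both stop at follow-up on Day 10.

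Two things follow. First, for non-referred children the length of observation is set by when the caregiver was reached, so a difference in call timing between periods would enter the pre-post contrast. Under the plan's 3% referral assumption, that branch holds about 100 - 3 = 97% of children at baseline. Second, the horizon differs by referral status, which the intervention is meant to change.

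This is the first-listed secondary outcome. SAP 6.5 also reports secondary hospitalisations as harms, so the same problem would arise there if the same coding is reused.

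**Working it through.** **1. The rule as written.** Let d be the admission day. SAP 6.1.1 treats admission on Day 0 or Day 1 as within 24 hours.

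- As written: count if (not referred) OR (1 < d <= 7).
- Limit on both branches: count if (d <= 7) AND (not referred OR d > 1).

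| Child | Days counted, as written | Days counted, limit on both branches |
|---|---|---|
| Not referred | 0-30 at the outer bound (31 days) | 0-7 (8 days) |
| Referred | 2-7 (6 days) | 2-7 (6 days) |

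The difference is Days 8-30, 23 calendar days, in non-referred children only. The SAP wording leaves open whether Day 30 itself is kept.

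**2. Can the sentence be read so that the 7-day limit covers both branches?** If it did, the 24-hour condition attached to it would naturally cover both as well. Same-day and next-day admissions without referral would then be excluded, although the definition in the same section and Protocol 6.4.1 count them. Neither natural reading gives the intended outcome.

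**3. Size.** The documents state no figure to reproduce. They give no admission rates and no distribution of call days, so all inputs here are assumptions: a share f of calls late at mean day D, and a daily admission hazard after Day 7 equal to r times the earlier hazard. The figures concern admissions of non-referred children.

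Relative over-count = f x r x (D - 7)/7, with D = 20, so (20 - 7)/7 = 13/7 = 1.857.

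| f | r = 1.0 | r = 0.1 |
|---|---|---|
| 5% | 9.3% | 0.9% |
| 10% | 18.6% | 1.9% |
| 20% | 37.1% | 3.7% |

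Apparent post/pre ratio under no effect, with 5% late calls pre and 15% post:

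- r = 1.0: (1 + 0.15 x 1.857)/(1 + 0.05 x 1.857) = 1.279/1.093 = 1.17
- r = 0.1: (1 + 0.15 x 0.1857)/(1 + 0.05 x 0.1857) = 1.0279/1.0093 = 1.02

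Taking Days 0-7 as eight calendar days changes the r = 1.0 results to 0.10 x 13/8 = 16% and 1.244/1.081 = 1.15.

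**4. Calls made on schedule.** The formula above ignores admissions on Days 8-10 picked up by calls inside the window. For a non-referred child called on day c, the counted admissions relative to Days 0-7 are (8 + r x (c - 7))/8:

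| Call day | r = 0.1 | r = 1.0 |
|---|---|---|
| 10 | 1.04 | 1.38 |
| 14 | 1.09 | 1.88 |
| 30 | 1.29 | 3.88 |

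These are per-child figures for a call on that day, not study averages.

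For the composite outcome all these figures are diluted, because deaths and admissions of referred children are already limited to Day 7.

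**The case against.** The strongest reply is that the intention is plain. The outcome is named by Day 7 in both documents, children without data are assumed not hospitalised by Day 7, and Protocol 7.1.1 describes Day 0 to Day 7 data. SAP 1.1 says the plan follows the protocol unless it states otherwise, and no departure is declared here. That stands as evidence of intent: a reader might infer that the SAP turned this into a 30-day outcome, and the documents do not support that. It does not repair the rule, because an analyst who codes the sentence gets a different endpoint.

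The second reply is that Day 30 overstates the reach. Calls are planned for Day 7, with attempts on the next three days. This stands: Day 30 is only an outer bound. How far the Day 7 form would record later admissions cannot be checked from these documents, although hospitalised status at a late call remains one route.

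The third concerns size. A constant hazard to Day 20 after an acute illness is at the high end, and no passage supports a tripling of late calls between periods. A reader might take 19% or 1.17 as the expected bias; they are upper ends of an assumed range. The effect of children changing branch is not quantified. The planned shift is 4.5 - 3 = 1.5 percentage points.

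Finally, this is a secondary outcome, modelled only if numbers allow. Both primary outcomes are assessed at Day 0 and are unaffected.

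**Conclusion.** The counting rule is wrong as written and should be corrected before analysis. It contradicts the Day 7 horizon of its own outcome and gives referred and non-referred children different windows. That conclusion rests on the text alone.

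The size rests on assumptions. With 10% of calls late at a mean of Day 20, the over-count of unreferred admissions is about 2% to 19% as the later hazard runs from 0.1 to 1.0 times the earlier one. With 5% late calls pre and 15% post, a null effect shows as about 1.02 to 1.17. Other late-call shares move these figures in proportion. Bias in the pre-post contrast through call timing requires that timing to differ between periods, which the documents do not report. The point reaches a key secondary outcome and possibly the harms summary, not the primary outcomes.

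**What to change.** Reword the hospitalisation rule in SAP 6.1.2.1 to: admission date within 7 days of Day 0 (7th day included) AND (not referred at Day 0 OR admission after 24 hours of Day 0). This applies to every child, whatever the call date.

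Keep the existing SAP 6.1.1 rule for implausible admission dates.

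Add a rule for missing admission dates. The present rule counts a non-referred child with a reported admission but no date. The reworded rule would drop that child, and SAP 6.1.1 deals only with implausible dates. One option is to count a reported admission with no date if the assessment was made by Day 10, with a sensitivity analysis that excludes it.

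State whether the harms summary uses the same definition.

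The cost is one reworded sentence, one added rule and one small sensitivity analysis. No new data are needed, since the SAP already relies on admission and assessment dates.

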6.1.2.3 Average length of stay (in days) of children admitted to hospital

Length of stay is defined as hospitalisation duration in days as reported by the caregiver at Day 7. If a child is hospitalised twice, the first hospitalisation will be used and second hospitalisations will be reported separately. The denominator will be all hospitalised children.

6.1.2.4 Proportion of children referred by a primary healthcare provider to a higher level of care at Day 0 consultation

All children who received a referral advice (as per definition above) at Day0 will be counted in the numerator. The denominator will be all children recruited.

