7.1.1 Quasi-experimental pre-post study

For each participant enrolled in the quasi-experimental pre-post study, data will be captured during the pre- and post-intervention periods according to the different assessments and Case Report Forms (CRFs) described in the visit schedule displayed in **Tab. 4**. A description of the variables collected in each CRF is available in the appendix.

Health facility visits

Quantitative research assistants will use an EDC mobile application to enter the research data of enrolled participants. The quantitative research assistant will collect from the caregiver screening information, information on care seeking behaviour, transport and costs, and clinical presentation and medical history. A number of in-depth sociodemographic and household variables will also be collected either as surrogate measures of household wealth, or known to be associated with health-seeking behaviour and / or child mortality (including maternal

education). Household wealth indicators were selected from DHS and other surveys in the study countries as those which best estimate wealth index that can be directly collected from the mother / caregiver and with a reasonable time vs. reliability trade-off. Data on laboratory investigations (if performed), final diagnosis, prescribed medication, referral or follow-up advice will be extracted from clinical notes and / or facility registers. Quantitative research assistants will seek clarification from healthcare providers only in cases where these variables are not clear from the records. Personally identifiable information (PII), including participant's name and date of birth, as well as caregiver's phone number and physical address, will be collected for linking data and detecting possible duplicates and carrying out the study follow-up.

During the post-intervention period, the research data of participants enrolled in the study will be linked with their CDSA consultation data. Additional information on oxygen saturation will be collected as recorded in clinical notes and / or facility registers. Pulse oximeter device savings will be cross-checked by quantitative research assistants at the end of the consultation where possible.

Follow-up

Quantitative research assistants will conduct the phone follow-up interviews using an EDC mobile application. Personally identifiable information (PII) will be used for contacting caregivers. A window of +3 days (Day 7 to Day 10) applies to Day 7.

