Data that will be collected at Day 7 follow-up will include cure status (recovery from illness as reported by the caregiver), hospitalisation and death between Day 0 and Day 7. If appropriate, name of the referral facility and duration of hospitalization will be collected to facilitate the retrospective data collection at referral hospital level.

Higher level of care visit

Data collection at this level of care will be conducted retrospectively. A quantitative research assistant using the EDC mobile application will collect data from referral facility records, registries and discharge summaries for children whose caregiver reported at Day 7 phone follow-up that they attended a government-designated referral facility between Day 0 and Day 7. This includes attendance to hospital or emergency / inpatient area of a larger primary or secondary care facility (e.g., study facilities that can admit paediatric patients). Personally identifiable information will be collected to cross-check the identity of the patients. Arrival date and time, basic clinical information on arrival and, if admitted, admission and discharge diagnosis and admission duration will be collected. If available, data on oxygen saturation at admission, oxygen administration and intensive care unit (ICU) admission and duration will also be recorded.

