6.2 Analysis Methods

6.2.1 Analytical Methods

For the primary analysis, pre-intervention and post-intervention periods will be defined as follow:

Pre-intervention period: from the date of data collection start to the date healthcare providers left the facilities for training on the intervention

Post-intervention period: from the date healthcare providers returned to the facilities after training and the devices was delivered to the facilities to the end of data collection

As training was staggered for the facilities, the definitions above will be applied at the facility level.

Outcomes will be described for each time period using summary statistics. In particular, counts and percentages will be used for binary variables and reported with one decimal place; mean and standard deviation (SD) or median (IQR) for continuous variables depending on their

distribution. Mean and median will be displayed with one decimal place and SD and IQR will be presented with two decimal places.

The two primary outcomes will be assessed using a random effects logistic regression model with the cluster included as a random effect. If convergence issues arise due to sparse data, clusters may be dropped or combined to higher grouping level (e.g. district).

Results will be reported with odds ratios, risk differences and their associated 95% confidence intervals (CI).

Secondary outcomes and other binary outcomes of interest will be evaluated in the same way.

Other continuous outcomes of interest will be assessed using random effects linear regression model with the cluster included as a random effect. Results will be reported in terms of adjusted mean differences with associated 95% CIs.

Modelling of secondary outcomes will be performed if numbers allow.

Further exploratory analysis, including interrupted time series analysis to assess change over time and data linked between the quasi-experimental pre-post study and the SPA and time-flow studies. These fall outside the scope of this SAP and will be detailed in a separate document.

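### Length of stay is averaged from the caregiver's Day 7 report with no rule for children still in hospital, so the mean is biased down and depends on admission day and call day.

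*SAP*

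**What the plan says.** SAP 6.1.2.3 fixes the source: "Length of stay is defined as hospitalisation duration in days as reported by the caregiver at Day 7". The first hospitalisation is used, and "The denominator will be all hospitalised children".

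SAP 6.1.1 decides who is hospitalised. A child qualifies if he or she went to a hospital and "was admitted overnight or if his/her status at the time of follow-up is" hospitalised. Stays still open at the call are therefore in the denominator by definition.

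On timing, Protocol 7.1.1 states: "A window of +3 days (Day 7 to Day 10) applies to Day 7". SAP 6.1.1 adds that where several assessments exist "the most recent follow-up assessment will be used", and that "assessments conducted far beyond the expected follow-up time will be dropped, i.e. 30 days from Day 0".

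On analysis, SAP 6.2.1 states: "Other continuous outcomes of interest will be assessed using random effects linear regression model with the cluster included as a random effect", reported as an adjusted mean difference. The descriptive summary may be a mean or a median, depending on the distribution.

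The protocol also has a second source. For children reported to have attended a government-designated referral facility, research assistants go back to that facility's records, and "admission and discharge diagnosis and admission duration will be collected" (Protocol 7.1.1, higher level of care visit). SAP 6.1.2.3 does not use it.

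**The concern.** The longest stay that a caregiver can report is the number of days between admission and the call. A child admitted on Day 5 and called on Day 7 contributes at most two days, whatever the true stay. Neither document has a rule for such stays. The missing-data section (SAP 6.3) deals with children not reached, and the hospitalisation sensitivity analyses (SAP 6.2.4) vary the cut-off between primary and secondary hospitalisation. Neither touches duration. A linear model on the reported days treats an unfinished stay as a finished one.

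The pre-post comparison is exposed if the mix of admission days differs between periods. The study's own secondary outcomes separate admission within 24 hours after referral from later admission, so a shift in timing is something it sets out to measure. An earlier mix lengthens the observable window, and recorded stay rises even if true stay does not. A reader could take that for sicker children or a heavier load on hospitals.

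**Working it through.** The plan gives no mean, standard deviation or target difference for length of stay, so there is no figure to reproduce. The check asks how far the definition alone can move the recorded mean.

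**Formula.** For true stay L, admission day a and call day c, with an open stay entered as days so far:

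recorded stay = min(L, c − a)

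**Inputs from the documents.** Call due on Day 7 to Day 10; open stays included; means compared with no censoring.

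**Inputs assumed (not in the documents).** The distribution of L is the same in both periods. The share admitted on Day 0-1 is 50% before and 80% after, with the rest spread evenly over Day 2-6.

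**Hand check: every stay lasts exactly 5 days, call on Day 7.** Admission on Day 0, 1 or 2 is recorded as 5 days. Admission on Day 3, 4, 5 and 6 is recorded as 4, 3, 2 and 1.

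- Mean for Day 0-1 admissions: 5
- Mean for Day 2-6 admissions: (5 + 4 + 3 + 2 + 1)/5 = 3
- Before: 0.5 × 5 + 0.5 × 3 = 4.0
- After: 0.8 × 5 + 0.2 × 3 = 4.6

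The spurious rise is 0.6 days, and both periods fall short of the true 5. With every call on Day 10, the Day 2-6 mean becomes (5 + 5 + 5 + 5 + 4)/5 = 4.8. The recorded means are then 4.90 and 4.96, a rise of 0.06.

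**Simulation with variable stays.** L is lognormal with log-SD 0.7, rounded to whole days with a minimum of one. There were one million children per scenario, and the same admission shift was used.

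| Call | True mean (days) | Recorded before | Recorded after | Spurious rise | Still admitted at call, before / after | Rise if open stays are left out |
|---|---|---|---|---|---|---|
| Day 7 | 3 | 2.42 | 2.65 | 0.23 | 20.8% / 12.0% | 0.16 |
| Day 7 | 4 | 2.90 | 3.26 | 0.36 | 30.7% / 19.9% | 0.20 |
| Day 7 | 5 | 3.28 | 3.76 | 0.48 | 39.8% / 28.2% | 0.22 |
| Day 7 | 7 | 3.80 | 4.45 | 0.65 | 55.1% / 43.9% | 0.23 |
| Day 7-10 | 3 | 2.66 | 2.79 | 0.13 | 11.9% / 7.0% | 0.12 |
| Day 7-10 | 4 | 3.28 | 3.51 | 0.23 | 19.7% / 12.9% | 0.17 |
| Day 7-10 | 5 | 3.78 | 4.11 | 0.33 | 27.7% / 19.5% | 0.21 |
| Day 7-10 | 7 | 4.54 | 5.04 | 0.50 | 42.5% / 33.5% | 0.25 |

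With completed stays the difference between periods is zero by construction. The last column matters because the SAP does not say whether an open stay is entered as days so far or left missing. The direction is the same either way, but the bias is smaller when open stays are missing.

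**The case against.** **Size.** A reader might infer an artefact of about one day. With exponential stays of mean μ and window w, the recorded mean is μ(1 − e^(−w/μ)). For μ = 5 and a Day 7 call this gives 3.77 days for a Day 0 admission and 2.75 for a Day 3 admission. That compares two admission days, not two periods. If 30 points of admissions move from Day 3 to Day 0, the effect on the period mean is 0.3 × 1.0, or about 0.3 days. If every call were on Day 10, the gap falls to 0.56 and the effect to about 0.17. This objection stands, and the one-day reading should not be used.

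**Direction.** A reader might also infer that the intervention will produce a false rise. The documents do not say that it is meant to bring admissions forward. Protocol 6.4.1 gives the aim as raising the referral rate of children with severe disease. That could add admissions as well as move them, and so change case mix and true stay. The rise is conditional, and the net observed change could go either way. The downward bias within each period does not depend on this.

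**Call timing.** The window to Day 10, the retention of assessments up to 30 days and the use of the most recent one all reduce truncation. They do not remove it, and they make the result depend on when calls were made, which may differ between periods.

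**Records.** It is tempting to say that the hospital records hold the full stay for everyone. They cover government-designated facilities (Protocol 7.1.1) within the study area, and depend on matching identities (Protocol 7.2.4). Private, out-of-area and unmatched admissions are missing, and a retrieval rate that differs by period would bring its own bias.

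**Descriptive median.** SAP 6.2.1 allows a median, which is less sensitive to cut-off long stays. The modelled mean difference remains exposed.

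**Conclusion.** The point holds in a limited form. Applied as stated, the definition gives a truncated mean that depends on admission day and call day. It is biased down in both periods whenever any child is still admitted at the call.

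A spurious difference between periods needs a further condition: a change in the mix of admission days (or of call days) with case mix and true stay unchanged. Under the assumed move from 50% to 80% early admission and true means of 3 to 7 days, it is about 0.2 to 0.65 days with Day 7 calls and 0.13 to 0.50 days with calls over Day 7 to 10. If open stays are simply missing, it is 0.12 to 0.25 days across the same scenarios. It shrinks towards nothing if almost all stays are short.

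The stay distribution and the timing shift are assumptions, so these are illustrations, not predictions. Length of stay is listed among the other outcomes of interest and has no part in the sample size, so the consequence is low.

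**What to change.** In SAP 6.1.2.3 and 6.2.1:

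- Treat a stay open at the call as right-censored at the call date. Report a restricted mean or Kaplan-Meier median by period in place of the plain mean difference.
- State how in-hospital death is handled, either as an end of stay or as a competing event.
- Where a matched referral-facility record gives the completed admission, use its duration to complete the stay. The SAP already relies on hospital records for oxygen (6.1.5.4), and the economic analysis uses hospital length of stay (Protocol 7.3.4).
- Report by period the share still admitted at the call and the share with a record found.
- Add a sensitivity analysis using caregiver reports only, censored at the call, because record coverage is partial and may differ between periods.

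The cost is a little more analysis work and a mix of two data sources, which the last two items make visible. No new data collection is needed.
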